11. MEASUREMENT OF EFFECT

11.1 Antitumor Effect – Solid Tumors

For the purposes of this study, patients should be re-evaluated for response every 8 weeks. In addition to a baseline scan, confirmatory scans should also be obtained at least 4 weeks following initial documentation of objective response.

Response and progression will be evaluated in this study using the new international criteria proposed by the revised Response Evaluation Criteria in Solid Tumors (RECIST) guideline (version 1.1) [Eur J Ca 45:228-247, 2009]. Changes in the largest diameter (unidimensional measurement) of the tumor lesions and the shortest diameter in the case of malignant lymph nodes are used in the RECIST criteria.

11.1.1 Definitions

Evaluable for toxicity. All patients will be evaluable for toxicity from the time of their first treatment with navitoclax and/or trametinib.

Evaluable for objective response. Only those patients who have measurable disease present at baseline, have received at least one cycle of therapy, and have had their disease re-evaluated will be considered evaluable for response. These patients will have their response classified according to the definitions stated below. (Note: Patients who exhibit objective disease progression prior to the end of cycle 1 will also be considered evaluable.)

Evaluable Non-Target Disease Response. Patients who have lesions present at baseline that are evaluable but do not meet the definitions of measurable disease, have received at least one cycle of therapy, and have had their disease re-evaluated will be considered evaluable for non-target disease. The response assessment is based on the presence, absence, or unequivocal progression of the lesions.

11.1.2 Disease Parameters

Measurable disease. Measurable lesions are defined as those that can be accurately measured in at least one dimension (longest diameter to be recorded) as \geq 20 mm by chest x-ray or as \geq 10 mm with CT scan, MRI, or calipers by clinical exam. All tumor

p: Off study procedures should be performed within 14 days of last dose. Patients will be followed until the resolution or stabilization of all study-related toxicity and for a minimum of 30 days after removal from study or until death, whichever occurs first. Patients removed from study for unacceptable adverse event(s) will be followed until resolution or stabilization of the adverse event.

measurements must be recorded in millimeters (or decimal fractions of centimeters).

Note: Tumor lesions that are situated in a previously irradiated area might or might not be considered measurable. *If the investigator thinks it appropriate to include them, the conditions under which such lesions should be considered must be defined in the protocol.*

Malignant lymph nodes. To be considered pathologically enlarged and measurable, a lymph node must be ≥ 15 mm in short axis when assessed by CT scan (CT scan slice thickness recommended to be no greater than 5 mm). At baseline and in follow-up, only the short axis will be measured and followed.

Non-measurable disease. All other lesions (or sites of disease), including small lesions (longest diameter <10 mm or pathological lymph nodes with ≥10 to <15 mm short axis), are considered non-measurable disease. Bone lesions, leptomeningeal disease, ascites, pleural/pericardial effusions, lymphangitis cutis/pulmonitis, inflammatory breast disease, and abdominal masses (not followed by CT or MRI), are considered as non-measurable.

Note: Cystic lesions that meet the criteria for radiographically defined simple cysts should not be considered as malignant lesions (neither measurable nor non-measurable) since they are, by definition, simple cysts.

'Cystic lesions' thought to represent cystic metastases can be considered as measurable lesions, if they meet the definition of measurability described above. However, if non-cystic lesions are present in the same patient, these are preferred for selection as target lesions.

Target lesions. All measurable lesions up to a maximum of 2 lesions per organ and 5 lesions in total, representative of all involved organs, should be identified as **target lesions** and recorded and measured at baseline. Target lesions should be selected on the basis of their size (lesions with the longest diameter), be representative of all involved organs, but in addition should be those that lend themselves to reproducible repeated measurements. It may be the case that, on occasion, the largest lesion does not lend itself to reproducible measurement in which circumstance the next largest lesion which can be measured reproducibly should be selected. A sum of the diameters (longest for non-nodal lesions, short axis for nodal lesions) for all target lesions will be calculated and reported as the baseline sum diameters. If lymph nodes are to be included in the sum, then only the short axis is added into the sum. The baseline sum diameters will be used as reference to further characterize any objective tumor regression in the measurable dimension of the disease.

Non-target lesions. All other lesions (or sites of disease) including any measurable lesions over and above the 5 target lesions should be identified as **non-target lesions** and should also be recorded at baseline. Measurements of these lesions are not required, but

the presence, absence, or in rare cases unequivocal progression of each should be noted throughout follow-up.

11.1.3 Methods for Evaluation of Measurable Disease

All measurements should be taken and recorded in metric notation using a ruler or calipers. All baseline evaluations should be performed as closely as possible to the beginning of treatment and never more than 4 weeks before the beginning of the treatment.

The same method of assessment and the same technique should be used to characterize each identified and reported lesion at baseline and during follow-up. Imaging-based evaluation is required in this study.

Conventional CT: This guideline has defined measurability of lesions on CT scan based on the assumption that CT slice thickness is 5 mm or less. If CT scans have slice thickness greater than 5 mm, the minimum size for a measurable lesion should be twice the slice thickness. CT is the preferred imaging modality in this study and should be used as the primary method of disease assessment unless otherwise measurable lesions are not able to be adequately assessed by CT scan, in which case one of the following imaging modalities can be used instead. However, the same imaging modality used at baseline should be used for evaluation of measurable disease throughout the study.

MRI: Use of MRI is acceptable in situations in which lesions are not adequately assessable by conventional CT scanning. Use of MRI remains a complex issue. MRI has excellent contrast, spatial, and temporal resolution; however, there are many image acquisition variables involved in MRI, which greatly impact image quality, lesion conspicuity, and measurement. Furthermore, the availability of MRI is variable globally. As with CT, if an MRI is performed, the technical specifications of the scanning sequences used should be optimized for the evaluation of the type and site of disease. Furthermore, as with CT, the modality used at follow-up should be the same as was used at baseline and the lesions should be measured/assessed on the same pulse sequence. It is beyond the scope of the RECIST guidelines to prescribe specific MRI pulse sequence parameters for all scanners, body parts, and diseases. The same type of scanner should be used and the image acquisition protocol should be followed as closely as possible to prior scans. Body scans should be performed with breath-hold scanning techniques, if possible.

PET-CT: At present, the low dose or attenuation correction CT portion of a combined PET-CT is not always of optimal diagnostic CT quality for use with RECIST measurements. However, if the site can document that the CT performed as part of a PET-CT is of identical diagnostic quality to a diagnostic CT (with IV and oral contrast), then the CT portion of the PET-CT can be used for RECIST measurements and can be used interchangeably with conventional CT in accurately measuring cancer lesions over

Version Date: July 22, 2022

time. Note, however, that the PET portion of the CT introduces additional data which may bias an investigator if it is not routinely or serially performed.

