3. PATIENT SELECTION

3.1 Eligibility Criteria

- 3.1.1 Patients must have histologically- or cytologically-confirmed diagnosis of KRAS or NRAS mutation-positive malignancy that is metastatic or unresectable and for which standard curative measures do not exist or are no longer effective. Patients must have activating mutations affecting codons 12, 13, 61, or 146 as determined in a CLIA certified lab to be eligible for this study.
- 3.1.2 Patients must have measurable disease by RECIST, defined as at least one lesion that can be accurately measured in at least one dimension (longest diameter to be recorded for non-nodal lesions and short axis for nodal lesions) as ≥20 mm by chest x-ray or as ≥10 mm with CT scan, MRI, or calipers by clinical exam. See Section 11 for the evaluation of measurable disease.

Version Date: July 22, 2022

3.1.3 Participants must have received at least one line of prior systemic chemotherapy and must have experienced documented radiographic progression or intolerance on this therapy.

- 3.1.4 Paired pre-treatment and post-treatment biopsies are required for all patients on Part 1 and first 15 patients in Part 2. Participants must have available archival tumor tissue (at least 20 unstained slides.) If archival tissue is not available or is found not to contain tumor tissue, a fresh biopsy is required. If a patient is having a tumor biopsy, less than 20 unstained slides are acceptable with approval of the PI. Biopsies will only be performed in a given patient if they are not deemed to involve unacceptable risk based on the sites of disease and other concurrent medical conditions.
- 3.1.5 Age \geq 18 years.

Because no dosing or adverse event data are currently available on the use of trametinib in combination with navitoclax in patients <18 years of age, children are excluded from this study, but will be eligible for future pediatric trials.

- 3.1.6 ECOG performance status ≤ 1 (see Appendix A).
- 3.1.7 Life expectancy of greater than 3 months
- 3.1.8 Able to swallow and retain orally-administered medication and does not have any clinically significant gastrointestinal abnormalities that may alter absorption such as malabsorption syndrome or major resection of the stomach or bowels.

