10. STUDY CALENDAR

Baseline evaluations are to be conducted within 2 weeks prior to start of protocol therapy. Scans and x-rays, Echocardiogram or MUGA, and ophthalmic examination must be done ≤ 4 weeks prior to the start of therapy. In the event that the patient's condition is deteriorating, laboratory evaluations should be repeated within 48 hours prior to initiation of the next cycle of therapy. All study visits have a ± -3 day window after Cycle 2, Day 1.

Labs obtained on C1, D1 must re-meet eligibility criteria.

[#] Represents 14th day of trametinib dosing under Schedule C Trametinib dosing is always in the evenings. Timing is not adjusted on PK days

Part 1 (Phase 1b) Schedule A

	Pre- Study	C1D1	C1D7	C1D8	C1D15	C1D21	C1D22	C2D1	C2D15	C3D1, C4D1, etc	Off Study ^q
Trametinib				T	T	T	T	T	T	Т	
Navitoclax		L	L	N	N	N	N	N	N	N	
Informed consent a	X										
Demographics	X										
Medical history	X										
Concurrent meds	X	X								X	
Physical exam b	X	X		X	X		X	X	X	X	X
Vital signs c	X	X	X	X	X	X	X	X	X	X	X
Height	X										
Weight	X	X		X	X		X	X	X	X	X
Performance status	X	X		X	X		X	X	X	X	X
CBC w/diff, plts	X	X	X		X		X	X	X	X	X
Serum chemistry ^d	X	X	X		X		X	X	X	X	X
PT/PTT	X	X	X				X			X	X
Tumor Markers ^e	X							X		X	X
Urinalysis	X										
EKG ^f	X	X		X	X		X	X	X		
Echocardiogram or MUGA	X	Repeat	on C1D28				l.) Thereaft ine and foll			reeks (use	
Ophthalmology exam	X		Rej	peated as	needed onl	y if patient	experience	s vision cl	hanges		
Adverse event evaluation		X								X	X
Radiologic evaluation/Tumor measurements	X	Cycle 1	Radiologic measurements (by CT or MRI) should be performed every 8 weeks following Cycle 1 Day 1. Tumor measurements are repeated every 8 weeks. Documentation (radiologic) must be provided for patients removed from study for progressive disease. h								
B-HCG i	X										

92

Version Date: July 22, 2022

Tumor biopsy	X j				Xk			
PK blood draw ^l		Xm	Xm	X ⁿ	Xn	Xº	X^{l}	
Archival Tissue	Xp							

- T: Trametinib. Dose as assigned; dose first in morning on empty stomach, at least 1 hour before food (there are no hematologic paramaters that must be met to continue dosing with trametinib at the beginning of each cycle.)
- N: Navitoclax. Dose as assigned; dose second in morning with food, at least 1 hour after trametinib
- L: Lead-in dose of navitoclax. 150 mg daily in morning for 7 days, dosed as above.
- a: Informed consent can be signed within 28 days of C1D1.

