13.5.2 Evaluation of Response

All patients included in the study must be assessed for response to treatment, even if there are major protocol treatment deviations or if they are ineligible. Each patient will be assigned one of the following categories: 1) complete response, 2) partial response, 3) stable disease, 4) progressive disease, 5) early death from malignant disease, 6) early death from toxicity, 7) early death because of other cause, or 9) unknown (not assessable, insufficient data). [Note: By arbitrary convention, category 9 usually designates the "unknown" status of any type of data in a clinical database.]

All of the patients who met the eligibility criteria (with the possible exception of those who received no study medication) should be included in the main analysis of the response rate. Patients in response categories 4-9 should be considered to have a treatment failure (disease progression). Thus, an incorrect treatment schedule or drug administration does not result in exclusion from the analysis of the response rate. Precise definitions for categories 4-9 will be protocol specific.

All conclusions should be based on all eligible patients. Sub analyses may then be performed on the basis of a subset of patients, excluding those for whom major protocol deviations have been identified (*e.g.*, early death due to other reasons, early discontinuation of treatment, major protocol violations, etc.). However, these sub analyses may not serve as the basis for drawing conclusions concerning treatment efficacy, and the reasons for excluding patients from the analysis should be clearly reported. The 95% confidence intervals should also be provided.

REFERENCES

Balagula, Y., K. Barth Huston, K.J. Busam, *et al.* (2010). Dermatologic side effects associated with the MEK 1/2 inhibitor selumetinib (AZD6244, ARRY-142886). *Invest New Drugs*. 29:1114-1121.

Bekaii-Saab, T., M.A. Phelps, X. Li, *et al.* (2011). Multi-institutional phase II study of selumetinib in patients with metastatic biliary cancers. *J Clin Oncol.* 29:2357-2363.

Bendell, J., P. LoRusso, E. Kwak, *et al.* (2011). Clinical combination of the MEK inhibitor GDC-0973 and the PI3K inhibitor GDC-0941: A first-in-human phase Ib study in patients with advanced solid tumors. *AACR Meeting Abstracts*. Abstract LB-89.

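### A patient whose only measurable lesion can be measured by calipers but not on CT or MRI is eligible, yet has no permitted method for scoring a partial response and defaults to failure.

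*Combined protocol and SAP*

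**What the plan says.** All references are to the combined protocol and SAP.

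- **Entry (3.1.2).** Measurable disease means at least one lesion of "≥20 mm by chest x-ray or as ≥10 mm with CT scan, MRI, or calipers by clinical exam". CT or MRI measurability is not required.
- **Measurability and target lesions (11.1.2).** The definition repeats the caliper route ("with CT scan, MRI, or calipers by clinical exam"). Measurable lesions, up to two per organ and five in total, are to be target lesions, with a preference for those that can be measured reproducibly.
- **Method (11.1.3).** "Imaging-based evaluation is required in this study". Also: "CT is the preferred imaging modality in this study and should be used as the primary method of disease assessment". Where CT cannot adequately assess an otherwise measurable lesion, the section turns to the imaging modalities described after it, which are MRI and PET-CT. It adds: "The same method of assessment and the same technique should be used to characterize each identified and reported lesion at baseline and during follow-up".
- **Calendars (Section 10).** "Radiologic measurements (by CT or MRI) should be performed every 8 weeks". The same row is marked pre-study. No calendar names a caliper measurement.
- **Analysis (13.5.2).** Eligible patients belong in the main response analysis, and conclusions rest on all of them. Categories 4 to 9, which include unknown or not assessable, count as treatment failure.

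**The concern.** The entry rule and the response rule use different lists of methods. Calipers are enough to admit a patient and to define a target lesion, but they are not among the methods given for evaluating response. Partial response needs a 30% fall in the sum of target-lesion diameters (11.1.4.1). For a lesion that CT and MRI cannot measure, the plan gives no permitted way to obtain that sum at follow-up.

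If the rules are applied as written, a patient whose skin lesion clearly shrinks can end as unknown, and so as a failure. The bias runs one way, against the regimen. It matters most where one response decides: a cohort closes if none of the first 12 patients responds. Superficial disease is plausible in Cohort 4 (the remaining NRAS-mutant tumours, Section 5.1.2), because Section 2.4 names melanoma among the tumours of interest and Section 2.1 puts NRAS mutation at about 20% of melanoma. Sites that read the rule differently could also score the same patient differently.

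**Working it through.** **Step 1. Follow one patient through the text.** Take a single 15 mm skin nodule that calipers can measure and CT and MRI cannot.

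| Step | Section | Result |
|---|---|---|
| Measurable at entry? | 3.1.2, 11.1.2 | Yes, at least 10 mm by calipers |
| Target lesion? | 11.1.2 | Yes, the only measurable lesion |
| Follow-up method? | 11.1.3, calendars | CT, MRI or PET-CT; none measures it |
| Partial response? | 11.1.4.1 | Needs a sum of diameters; none available |
| In the denominator? | 13.5.2 | Yes, as an eligible patient |
| Default score? | 13.5.2 | Unknown (category 9), counted as failure |

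**Step 2. Reproduce the plan's own figures (13.1.2).** Inputs: 12 patients in stage 1, continue with at least 1 response; 13 more; promising with at least 3 of 25; rates 5% and 17%. With X1 ~ Bin(12, p) and X2 ~ Bin(13, p),

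P(promising) = P(X1=1)·P(X2≥2) + P(X1=2)·P(X2≥1) + P(X1≥3).

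- p = 0.05: 0.3413 × 0.1354 + 0.0988 × 0.4867 + 0.0196 = 0.114 (stated false-positive rate 11%).
- p = 0.17: 0.2627 × 0.6751 + 0.2960 × 0.9113 + 0.3344 = 0.781, so the false-negative rate is 21.9% (stated 22%).
- Early stopping at 5%: 0.95^12 = 0.540 (stated 54%).

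All three agree with the plan.

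**Step 3. Hypothetical cost of unscorable patients.** The number k of such patients is not in the documents and is assumed here. Thresholds stay fixed and the remaining patients respond at 17%.

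| Assumed k of 25 | Placement | Power at 17% |
|---|---|---|
| 0 | none | 78.1% |
| 1 | stage 1 (11 scorable) | 75.1% |
| 1 | stage 2 (12 scorable) | 76.4% |
| 1 | spread, rate 0.17 × 24/25 = 0.1632 | 75.7% |
| 2 | one in each stage | 73.2% |
| 2 | spread, rate 0.17 × 23/25 = 0.1564 | 73.0% |
| 3 | spread, rate 0.17 × 22/25 = 0.1496 | 70.1% |

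One such patient costs 78.1 − 76.4 = 1.7 points in stage 2 or 78.1 − 75.1 = 3.0 points in stage 1 (3.1 before rounding). One among the first 12 raises the chance of closing a cohort whose true rate is 17% from 0.83^12 = 10.7% to 0.83^11 = 12.9%. The false-positive rate at 5% does not rise: it falls from 11.4% to 10.2% (one in stage 1) or 10.5% (one in stage 2).

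**The case against.** The strongest reply is that the plan can be read as allowing calipers. Requiring imaging is not the same as forbidding clinical measurement. The same-method rule, applied to a caliper lesion, points to calipers. Section 11.1.3 mentions a ruler or calipers for recording measurements. The calendar row and footnote h mention tumour measurements alongside radiologic evaluation, and a complete physical exam including skin is due on Day 1 of every cycle. This shows that a caliper follow-up would be feasible. It does not show that one is permitted: no clinical-exam method is described, and lesions that CT cannot assess are sent only to other imaging.

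Three stronger readings are tempting, and the documents do not support them.

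- **That such patients can never be scored a response.** CT or MRI may well measure a lesion first found by calipers, and it is then an ordinary target lesion. If it is treated as non-target instead, complete response is arguable under 11.1.4.3. That table is headed for non-measurable disease, which this lesion is not under 11.1.2, and it offers no partial response.
- **That chest X-ray lesions have the same problem.** A lesion of at least 20 mm on X-ray can be measured on the baseline CT, where 10 mm is enough, and then followed by CT. The same-method rule is kept. X-ray is also imaging.
- **That mixed skin and CT-measurable disease must give an incomplete sum.** The preference for reproducibly measurable target lesions in 11.1.2 deals with most such cases.

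It may also be said that 11.1.1 restricts response evaluability to patients whose disease was re-evaluated. That is so, but 13.5.2 rests the conclusions on all eligible patients, so it does not remove the failure default.

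**Conclusion.** The inconsistency is real but narrow. It reaches only patients whose sole measurable disease can be measured by calipers and not on CT or MRI. For them the plan defines entry and target status, gives no permitted method for partial response, and defaults to failure.

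The numerical effect is small and conditional. No stated operating characteristic is wrong. A reader might take the figures in the table as the design's true false-negative rate; they are not, because k is assumed and zero is within the plausible range. Naming melanoma makes superficial disease plausible in Cohort 4 but says nothing about how often it is the only disease and cannot be imaged. If a cohort has none, nothing changes; each one would cost about 2 to 3 points of power at 17%. The case for correcting it is that the error could only count against the regimen and that the correction is nearly free.

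**What to change.** Make the method rule the same at entry and at follow-up. Either of these would do.

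1. **Imaging-measurable entry.** Require in 3.1.2 and 11.1.2 at least one lesion measurable on CT or MRI at baseline. Cost: wording in two sections, and exclusion of the few patients with caliper-only disease.
2. **Caliper follow-up.** State in 11.1.3 and in calendar footnote h that superficial target lesions not measurable on CT or MRI are measured by calipers at baseline and at every 8-week assessment, and enter the sum of diameters. Cost: wording in one section and one footnote (repeated in each calendar), and one extra measurement at a visit that already has a physical exam. Section 11.1.7 calls for independent review of responses in Part 2, so the text should also say what record of a caliper lesion the reviewer will see.

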11.1.4 Response Criteria

11.1.4.1 Evaluation of Target Lesions

Complete Response (CR): Disappearance of all target lesions. Any pathological lymph nodes (whether target or non-target) must have reduction in short axis to <10 mm.

Partial Response (PR): At least a 30% decrease in the sum of the diameters of target lesions, taking as reference the baseline sum diameters.

Progressive Disease (PD): At least a 20% increase in the sum of the diameters of target lesions, taking as reference the smallest sum on study (this includes the baseline sum if that is the smallest on study). In addition to the relative increase of 20%, the sum must also demonstrate an absolute increase of at least 5 mm. (Note: the appearance of one or more new lesions is also considered progressions).

Stable Disease (SD): Neither sufficient shrinkage to qualify for PR nor sufficient increase to qualify for PD, taking as reference the smallest sum diameters while on study.

